
Devices

1. * List each device in the study that will be evaluated for safety or effectiveness:

Device	Purpose	Type
View NeuroConn DC- Stimulator	An IDE application (G150197) was submitted to the FDA on August 14 (received by the FDA on September 9, 2015). The FDA has determined that the proposed study is a nonsignificant risk device study because it does not meet the definition of a significant risk (SR) device under §812.3(m) of the Investigational Device Exemption (IDE) regulation (21 CFR 812). The letter from the FDA is attached under the "other attachments section". Overall, there are no significant risks associated with tES as all risks are very unlikely and minimally serious. Several investigators have examined the safety aspects associated with transcranial direct current stimulation (tDCS). For example, Iyer et al. (2005), applied 1 and 2 mA anodal, cathodal, and sham DC stimulation to the left prefrontal cortex for 20 minutes while clinical EEG was recorded. Participants were encouraged to report any discomfort or subjective sensations while undergoing stimulation. These researchers observed no aversive EEG abnormalities resulting from DC stimulation, and no participants asked to stop the study or reported any significant discomfort. Differences in mood between sham and stimulation were assessed using the Visual Analog Mood Scale (VAMS) that measures subjective reports of anger, anxiety, confusion, energy, fright, happiness, sadness, tension, and tiredness. The investigators found no measurable effects of stimulation on participants' VAMS scores. Based on their findings, they conclude that limited exposure to direct current stimulation between 1 and 2 mA is a safe procedure in healthy participants. In another study conducted by Gandiga, Hummel, and Cohen (2006), tDCS and sham were compared in healthy volunteers and chronic stroke victims. Discomfort was measured using a 10 point scale, where 1 represented no discomfort and 10 represented extreme discomfort and pain. These researchers report transient and mild discomfort of sensations (12 on the 10 point scale) that weren't significant between sham and stimulation conditions, nor between healthy volunteers and stroke victims. Safety and tolerability of tES has also been examined in adults with schizophrenia (Brunellin et al., 2014), as well as childhood onset schizophrenia (Matai et al., 2011). tES in these studies was well tolerated by participants, and no adverse events were reported. Recently, safety of other forms of tES have been thoroughly examined. Chaieb et al. (2014) examined assessed safety aspects of Sinusoidal transcranial alternating current stimulation (tACS) by measuring neuronspecific enolase (NSE) levels, examining electroencephalogram (EEG) traces and analyzing anatomical data by using magnetic resonance imaging (MRI). tACS was delivered at 5 kHz applied for 10 min at 1 mA intensity over the hand area of the primary motor cortex. No changes were detected in NSE levels, no structural alterations were observed in the anatomical scans and no pathological changes were found in the EEG recordings. Additionally, Zaghi et al. (2010) administered various behavioral and neuropsychological tests during tACS. tACS was not associated with any cognitive adverse effects and had no harmful effects on motor function (Purdue Pegboard Test, Finger Tapping Test). Moreover, tACS was not associated with pain, mood, or anxiety. DCSTIMULATOR has a Maximum Voltage Limitation of +/- 20V. The output circuit of the constant current source of the DCSTIMULATOR is equipped with an electrical fuse which limits the current to 5 mA. Therefore, in any faulty condition and during normal operation, the fuse will become open circuit if the current exceeds 5 mA by a significant amount. The higher the current exceeds 5 mA the faster it will become open circuit. This means that it is impossible for the participant to receive a harmful level of current, even in cases of equipment malfunction. To avoid thermal discomfort and possible skin damage, the German authority (Bundesanstalt für Arzneimittel und Medizinprodukte) gives a limit of 0.1 mA/cm ² for DC current applications. The largest current density we will use here is 0.08 mA/cm ² . We will monitor participant discomfort throughout the administration of tES. If at any point the participant reports perceived heat, tingling, or itching at the site of the electrodes as 8 or higher on a 10 point scale, tES will be stopped immediately. The Co-I, [name], has administered tES to over 250 research participants in previous studies at the University of New Mexico, with only two adverse events, one of which was due to latex allergy, and the other was due to small electric shock caused by suboptimal equipment. Only the PI and trained research staff /Co-I's will administer tES here, and individuals with latex allergy will be excluded. The Neuroconn stimulator used here is robust, so we do not anticipate this to be a problem here.	Abbrevia

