Study Design and Procedures. Eighty (male=40, female=40) high treatment-interest daily smokers age 26-55 will be recruited from the local Pittsburgh community. As noted, past work has not revealed sex differences in CR, AAT, or tDCS training outcomes with smokers, but we will examine sex differences here. Participants will be screened via telephone interview, and again in person, for multiple measures including level of quit interest, assessed by asking subjects if they intend to quit smoking in the next 1, 3, 6, 12 months, longer, or never. Using a 2 x 2 design we will examine AAT (AAT, active control [AC]) X tDCS (active, sham) to reduce cue-induced craving and smoking topography, and attenuate behavioral and neurophysiological measures of attentional bias to combined personal smoking cues. We will also determine the impact of this novel CET methodology on daily smoking, intent and confidence to quit, and explore sex and other individual differences in the efficacy. Eligible participants will come to the laboratory and complete informed consent and further screening, including vision screening for sensory deficits that may affect cue reactivity and/or EEG testing, re-assessment of treatment interest and completion of forms. Participants will also undergo the semi-structured interview to identify the places of which to take pictures, and complete camera practice. After initial screening, participants will be randomized to one of the 4 groups (stratified by sex & age). Dropouts will be replaced but examined by AAT/tDCS group to assess tolerability. Groups include: 1) AAT + active (2.0 mA) tDCS, 2) AAT + sham (0.01 mA), 3) active control (AC) + active tDCS, or 4) AC + sham. Participants will participate in AAT/tDCS intervention sessions for 5 days over 3 weeks, but the over all study will be 10 visits total similar to our tDCS/schizophrenia study (DA0417742), and that by Mattai et al. Cue-induced craving, smoking topography, and attentional bias (reaction time & ERPs), as well as cigs/day intent to quit90 and confidence in quitting91 will be assessed at Week 1 Baseline sessions 1 & 2 and Re-test sessions 9 & 10 during Week 3. Cigs/day, intent and confidence to quit will be re-assessed during follow-up phone calls 1-week and 1-month post-training

3. Describe the primary and secondary study endpoints:

Primary:

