in this experimental study will be replaced. We will examine differential group dropout to assess tolerability of methods. Limited past work leads us to constrain our power analysis to AAT and/or tDCS for each variable, but we expect the synergistic effects of combined AAT + tDCS to be even greater, making these power analyses conservative. However, this exploratory work is not fully powered to detect significant interaction effects. Aim 1. Craving and Attentional bias. Assuming a Cohen's d effect size (ES) of 1.02- 1.57 based on prior literature, a multivariate $\alpha = .05$, and an R2 of .3 from other covariates in the model, we expect to have greater than 0.99 power to detect main effects of tDCS on cue-induced craving. Boggio et al.⁴¹ found an ES of $d=1.13$ for reduction in cue-induced craving via tDCS. Our pilot P300 EEG data from our current study in smokers with schizophrenia shows ES of $d=1.3$. AAT work indicates post-training

attentional approach bias reductions to smoking cues of $d=1.2629$, thus we expect greater than .80 power to detect changes in attentional bias. Aim 2. Smoking topography and cig/day. Based on our past cue studies, smoking topography to multiple cues are of similar magnitude to cue-induced craving ($d=.90$). Further, past tDCS studies of daily smoking outcome show an ES of 0.58100. Thus, with a multivariate of $\alpha=.05$, 20 subjects per group, and an R2 of .3, we expect greater than 0.84 power to detect an effect of tDCS on smoking behavior in both the MANCOVA assessing immediate effects on smoking behavior and the RM-MANCOVA assessing longitudinal effects on cig/day and intent & confidence to quit. Again, tDCS

+ AAT should enhance effects. Aim 3. Smoking prediction. Assuming $\alpha=0.17$ (conservative adjustment for 3 outcome variables) and controlling for other variables contributing an R2 of .3, we will have power greater than .99 to detect an R2 of 0.2422 or larger, in the model predicting smoking topography and cig/day from cue-induced craving and attentional bias change scores.

Research Activities

1. * Provide a detailed description of all research activities (including screening and follow-up procedures) that will be performed for the purpose of this research study. This description of activities should be complete and of sufficient detail to permit an assessment of associated risks.

The PI, Co-I's and Research Coordinators will be responsible for carrying out all the research activities.

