2. AAT + sham tDCS
3. AC + tDCS
4. AC + sham tDCS

The components of these groups are defined as:

- Approach/Avoidance Task (AAT): The participant will use a joystick to push and pull images in different directions on a computer screen.
- Transcranial Direct Current Stimulation (tDCS): is used to slightly change the way the brain works for a short time. One wet, thin sponge is placed on the participants head and another wet thin sponge is placed on their arm and connected to electrodes which will deliver a very weak electrical current. Before stimulation, their head and arm will be checked for any redness, irritation, or recent shaving of the head. If any of these are seen, we will exclude them from the study. Some participants may feel a slight painless tingling as the current begins, but the tingling should go away after a short time. tDCS will be given at 2.0 mA and stimulate the

dorsolateral PFC (dIFPC) the sham tDCS will be given at 0.01 mA. We will ask the participant at the beginning of and throughout the stimulation to report how much tingling they are feeling on a scale of 1 being "not at all" and 10 being "extreme". If at any point they are experiencing extreme discomfort, we will end the stimulation.

- Active Control (AC): The participant will assess the orientation of a picture and indicate it with a key press.
- Sham tDCS: Two wet, thin sponges are placed on the participants head and arm and the sponges will be connected to electrodes just as the actual tDCS but they will not deliver any electrical current.

Visits 2 and 9: During this visit the participant will have an attentional bias assessment while undergoing an electroencephalography (EEG).

- Attentional-Bias: You will be seated in front of a computer with a four-button color response box. Four different word lists of 15 words each will be presented in a random order with no repeats. For each trial, a cross appears in the center of the screen followed by one word from the list in one of four colors. You will press the button that matches the color in which the word appears.

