Storage Device	Description	Identifiable Data	Sensitive Data	De-Identified/Anonymous Data
View UPMC owned desktop, laptop or other device		no	no	yes
View UPMC: Departmental or Hospital Server		yes	yes	yes
View UPMC: OneDrive /Sharepoint		no	no	yes

5. * Select all technologies being used to collect data or interact with subjects: Technologies selected in this section may require a Vendor Security Risk Assessment, which can be requested [here](#).

Web-based site, survey, or other tool

Other

6. * Web Based Technologies – identify all web based technologies to be used to collect data during any phase of the research:

name	Identifiable
View Pitt Redcap Version	

7. * Other Technologies:

name	Identifiable
Digital Camera	no

Data Safety and Monitoring

1. * Describe your plan to periodically evaluate the data collected regarding both harms and benefits to determine whether subjects remain safe. The plan might include establishing a data monitoring committee and a plan for reporting data monitoring committee findings to the IRB and the sponsor:

DATA SAFETY AND MONITORING PLAN

The Principal Investigator, Drs. [name], and the Co-I [name] will ensure that there are no changes in the risk/benefit ratio throughout the duration of the proposed studies. Investigators and study personnel will meet weekly to discuss the progress of the study. Minutes of these meetings will be maintained in the study binder. At each meeting, the study goals will be discussed and any changes needed to the IRB application will be made.

Real-time safety monitoring. Our safety monitoring plan involves monitoring of adverse events at each lab visit during the study. Drs. [name] and [name] will be available at all times by phone/pager during all sessions if adverse events need to be addressed, as will Sr Research Coordinator [name]. In addition, subjects will be able to call if they experience adverse events while away from the lab, a procedure we have employed in past studies. The PIs and Co-Is will monitor the research literature tDCS to identify new findings regarding the overall safety and use with participants. However, no new risks are anticipated, as the overall risks associated with transcranial direct current stimulation (tDCS) are considered minimal or no significant risk.

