	Infrequent Risks	The risk associated with transcranial electrical stimulation is minimal. There is a small risk of skin irritation which is minimized by using saline water as the conductive medium, and through the monitoring of participant discomfort throughout the procedure. tDCS is seen as a non-invasive medical procedure, and the commonly reported side-effects in active vs. sham treatments are itching (39.3% vs 32.9%), tingling (22.2% vs 18.3%), headache (14.8% vs 16.2%), burning sensation (8.7% vs 10%), and discomfort (10.4% vs 13.4%). ¹⁰⁷ Redness at the electrode site has also been reported.
	Other Risks	No Value Entered

View	Research Activity	Cue-Reactivity
	Common Risks	Some of the stimuli used have been shown to significantly increase urge to smoke. The discomfort of increased urge to smoke is anticipated to dissipate fairly quickly, and over the course of the treatment may lead to less robust responses.
	Infrequent Risks	No Value Entered
	Other Risks	No Value Entered

View	Research Activity	Collection and storage of private information
	Common Risks	No Value Entered
	Infrequent Risks	There is a rare possibility of a breach of confidentiality, but we have safeguards in place to minimize that. All records related to your involvement in this research study will be stored in a locked file cabinet and all electronic records are password and firewall protected. Your identity on these records will be indicated by a case number rather than by your name, although we may use your initials on certain forms.
	Other Risks	No Value Entered

2. * Describe the steps that will be taken to prevent or to minimize risks:

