*** Describe the circumstances and any procedures for orderly termination:**
It is possible that the subject may be removed from the research study by the researchers if he/she is unable to perform any of the required tasks or does not show up for scheduled study visits. He/She will always be paid for a session she attended prior to being formally withdrawn from the study.

8. Describe procedures that will be followed when subjects withdraw from the research, including partial withdrawal from procedures with continued data collection and data already collected:

Research data will be kept and reviewed for an indefinite period of time. Research information collected before excusal or withdrawal from the study will continue to be used and disclosed by the investigators for the purposes described above.

Placebo Arm

1. * Is there a commonly used diagnostic/treatment approach that is currently recognized as being effective for the proposed subjects' disease or condition, and that will be withheld from subjects assigned to the placebo arm of this research study:

N/A - the proposed subjects are normal, healthy volunteers

2. Describe the commonly used diagnostic/treatment approaches that will be withheld from subjects assigned to the placebo arm of this research study:

3. Is enrollment into this study limited to individuals in whom the commonly used diagnostic/treatment approaches are known to be ineffective or intolerable?

4. Provide a scientific justification for the placebo-control arm of this research study:

This is a balanced 2 x 2 design to examine the impact of two new methods to reduce cue reactivity to personal smoking cues. The placebo arm allows us to examine the individual and combined impact of the two techniques and compare them with a time and contact control. The effectiveness of the techniques being examined, independently or in combination, as methods to reduce cue reactivity to personal smoking cues has yet to be examined, so a placebo comparison is warranted.

5. How long will subjects participate in the placebo arm? Justify why this duration is necessary:

They will be in the placebo arm for the duration of the study 10 sessions. There are also follow-up phone calls at 1 week and 1 month post-training. This allows the placebo arm to serve as a control for subject time and contact.

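### Dropout by group is the only planned between-arm measure of tolerability, so stimulation ended early in participants who keep attending would not be counted

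*Combined protocol and SAP*

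**What the plan says.** Tolerability is named as something to assess in two places, both using dropout. Study Design, item 2: "Dropouts will be replaced but examined by AAT/tDCS group to assess tolerability". Study Design, item 8: "We will examine differential group dropout to assess tolerability of methods". Dropout is not defined in either.

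Discomfort during stimulation is handled elsewhere:

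- Research Activities, item 1 (tDCS): "We will ask the participant at the beginning of and throughout the stimulation to report how much tingling they are feeling", on a scale from 1 to 10. Then: "If at any point they are experiencing extreme discomfort, we will end the stimulation".
- Devices, item 1: "If at any point the participant reports perceived heat, tingling, or itching at the site of the electrodes as 8 or higher" on a 10-point scale, stimulation is stopped immediately.

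Risk and Benefits, item 7 says researchers may remove a participant "if he/she is unable to perform any of the required tasks or does not show up for scheduled study visits". An early end to stimulation is not listed there.

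Data Safety and Monitoring, item 1 adds: "Our safety monitoring plan involves monitoring of adverse events at each lab visit during the study". It also provides for quarterly team review of adverse events, compliance and attrition. Participant compliance is described through attendance records. No comparison by arm is stated.

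**The concern.** The event that most directly shows poor tolerability of tDCS is a session in which stimulation had to be ended. As written, that event ends stimulation; whether it also ends participation is not stated. If the participant attends the remaining visits, the planned measure does not register it.

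The measure can also count the wrong thing. Research Activities, item 1 lists randomisation at visit 1, while stimulation and the AAT or control task run at visits 4 to 8. Someone lost in between adds to a group's dropout without having received either component.

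Two uses of the results are affected. Study Aims, item 1 says the trial is to guide a future RCT, and the planners of that trial will want to know how much of the stimulation was completed in each arm. In addition, participants are not to know their group, and craving and cigarettes per day are self-reported. A difference in sensation between active and sham would bear on whether masking held, but no masking check is planned.

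**Working it through.** **1. No figure to reproduce.** The plan gives no rate, margin or power for tolerability. The power figures in Study Design, item 8 all concern efficacy. The first part of the check is therefore a comparison of texts.

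**2. The texts side by side.**

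| Question | What the documents give |
|---|---|
| How is tolerability compared between arms? | Dropout by group (Study Design, items 2 and 8) |
| What happens on discomfort? | Stimulation is ended (Devices, item 1; Research Activities, item 1) |
| Does that end participation? | Not stated in either place |
| When may researchers remove someone? | Unable to perform tasks, or missed visits (Risk and Benefits, item 7) |
| Where do the ratings go? | Into the decision to stop; no endpoint or analysis in Study Design, items 3 or 8 uses them |
| What does compliance review cover? | Attendance records of participants and compliance records of staff; completed stimulation is not named |

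An early stop reaches the planned measure only if the participant also leaves the study.

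**3. How much a dropout comparison can show.** Item 8 plans 20 per group in four groups, so 2 × 20 = 40 active and 40 sham. Dropout rates are assumptions. Power is the sum, over all pairs of counts (a, b), of

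Bin(a; n, p1) × Bin(b; n, p2) × 1[Fisher two-sided p ≤ 0.05].

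Dropouts are replaced, so more than 80 will be randomised if any occur, and Study Design, item 1 lists 160 to be enrolled. The last column therefore takes 80 v 80 as an upper case.

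| Assumed dropout, sham v active | Expected number of 40 | Power, 40 v 40 | Power, 80 v 80 |
|---|---|---|---|
| 5% v 15% | 2 v 6 | 0.18 | 0.48 |
| 10% v 20% | 4 v 8 | 0.16 | 0.35 |
| 5% v 20% | 2 v 8 | 0.41 | 0.79 |
| 10% v 30% | 4 v 12 | 0.53 | 0.87 |

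At the planned size, even a threefold or fourfold difference in dropout would be missed about half the time or more. Only if nearly all 160 were randomised would the larger differences be reasonably detectable.

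**4. How many participants early stops could involve.** The documents give no stop rate. Let s be the chance of a stop at one session, and assume five sessions attended and independence between them. The chance of at least one stop is 1 − (1 − s)^5.

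- s = 1%: 1 − 0.99^5 = 0.049; 40 × 0.049 ≈ 2 active participants
- s = 2%: 1 − 0.98^5 = 0.096; 40 × 0.096 ≈ 4
- s = 5%: 1 − 0.95^5 = 0.226; 40 × 0.226 ≈ 9

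Those who kept attending would be absent from the dropout comparison. These are illustrations of scale, not predictions.

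**The case against.** The case for leaving the plan alone has several parts.

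- *Tolerability is not an aim or endpoint.* The plan says only that dropout will be examined and claims no powered test. This stands, and it limits the weight of the point. The power figures show how little a dropout comparison can reveal; they do not show that a promised test fails.
- *Safety is watched.* Adverse events are monitored at each lab visit and reviewed quarterly, and the ratings decide when to stop. This stands too. A reader might infer that the ratings go unused, which would be wrong. What is missing is a planned summary by arm.
- *An early stop may lead to exit.* Dropout is undefined, removal is allowed for inability to do the tasks, and Research Activities, item 1 excludes people with redness or irritation seen before stimulation. Some intolerance may therefore reach the dropout count. A reader might infer that every stopped participant is counted as tolerating tDCS and as fully dosed. The documents do not say so; the gap concerns those who keep attending.
- *Early stops may be rare.* Devices, item 1 reports two adverse events in over 250 earlier participants, and a cited study in which nobody asked to stop. Risk and Benefits, item 1 gives discomfort of 10.4% active v 13.4% sham. A reader might infer that stimulation will often fail to be completed; nothing in the documents supports that.
- *Delivered dose may already be logged.* The upload request in Research Activities, item 2 excludes case report forms, so the absence of a completion field cannot be inferred, nor that delivered dose will be unknown.

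It is also tempting to argue that the ratings are a more powerful measure than dropout. They measure a different thing, and the documents give no relevant difference for either, so the two powers cannot be ranked.

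**Conclusion.** The point holds in a limited form. Dropout by group is the only between-arm tolerability measure the plan names. It would miss early stops in participants who continue, and it mixes in losses before visit 4 that cannot reflect the training or stimulation. At 40 v 40 it is a weak signal: power is 0.16 to 0.53 over the assumed dropout rates, rising to 0.35 to 0.87 if all 160 listed enrolments were randomised. These figures rest on assumed rates. The finding about which measure is used rests on the text alone.

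The consequence is a less informative account of tolerability, stimulation received and masking for the future RCT. No efficacy conclusion depends on it. This is a low-cost improvement, not a flaw in the main analysis.

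**What to change.** In Study Design, items 2 and 8, define dropout and state that tolerability will be described by arm, over everyone randomised including those later replaced, by:

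1. participants, and sessions, with stimulation ended early;
2. sessions and stimulation time delivered, out of planned;
3. peak 1-10 sensation rating per session;
4. dropout, separating losses before the first stimulation session (visit 4) from later ones.

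Report item 3 for active v sham as indirect evidence on masking as well. It is indirect because the rating records sensation, not a guess at assignment.

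Before this table can be produced consistently, two sets of passages must be reconciled. The stop criterion is a rating of 8 or higher for heat, tingling or itching in Devices, item 1, but extreme discomfort alongside a tingling scale in Research Activities, item 1. Sham is 0.01 mA in Study Design, item 2 and in the tDCS description in Research Activities, item 1, but no current in the sham description in that same item. This point takes no position on which is right and proposes no stopping rule.

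Cost: recording completion, time delivered and peak rating per session where these are not already logged, and one descriptive table. The ratings are already asked for, so no new procedure for participants is needed.

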
interest. We anticipate similar results here, as well as reductions in cue-induced craving and smoking topography. Given that tDCS should enhance AAT learning, we also anticipate that AAT+tDCS may further reduce in these measures. We will also examine potential increases in Intent and Confidence to quit, the former shown to increase with AAT training and both previously associated with quit initiation and ability to abstain. These three measures will be assessed pre-post training and, to examine more prolonged effects, at 1-week and 1-month post-training. Sex and individual differences. Although past cue reactivity, AAT, and tDCS work has not revealed sex differences across outcome variables, we will specifically recruit equal numbers of male and female smokers to determine if sex, as well as other individual differences (e.g., age, FTND, years smoking) moderate AAT/tDCS efficacy on our more comprehensive set of outcomes, and thereby offer new information about for whom our novel methods may work best as a smoking treatment.

INNOVATION.

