*** Identify the subgroups and provide a justification:**

Children, individuals defined as under the age of 18, will not be included as it is illegal to sell cigarettes to minors in Pennsylvania. The safety and efficacy of tDCS has not been tested in pediatric smokers, and standard doses have not been established.

8. Describe the power analysis used and cite your method of statistical analysis.

If a power analysis is not possible, thoroughly justify the sample size required for the study, including appropriate literature citation (alternatively provide page reference in attached protocol):

Statistical design and power

This study uses a 2 x 2 AAT (AAT, active control[AC]) x tDCS (tDCS, sham tDCS) design to assess prepost training changes in cue-induced craving and smoking

topography (latency to light and puff volume during cue exposure) and attentional bias (reaction time and ERPs) to smoking-related cues, as well as daily smoking (cigarettes per day) and confidence and intent to quit. The primary analyses (Aims 1 and 2) will be evaluated via repeated measures multivariate analysis of covariance (RM-ANCOVA) and will test the main effects of AAT, tDCS, and their interaction on measures of craving, reaction time, P300 amplitude, controlling for baseline levels as covariates (Aim 1). This process will be repeated for Aim 2, where MANCOVA will test effects on latency to smoke, total puff volume, and cigs/day. An additional 2x2x3 repeated measures (RM-) MANCOVA will test group differences in cig/day and intent & confidence to quit

across time points (post-training, 1-week, and 1-month). For Aim 3, regression analysis will be used to examine if attenuation of cue-induced craving and attentional bias measures predict reductions in smoking topography and daily smoking and elevations in intention to quit and confidence to quit, while controlling for baseline levels of these variables. Exploratory analyses will probe whether sex and other individual differences (e.g., age, FTND) moderate the effects of AAT/tDCS training on all outcome variables.

Power is based on n=20 high treatment-interest smokers per group, with 4 experimental groups. Drop outs

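### The Aim 3 significance level is printed as 0.17 and called a conservative adjustment for three outcomes, but .05 adjusted for three outcomes is 0.0167; very probably a slip for 0.017

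*Combined protocol and SAP*

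**What the plan says.** All of this is in the combined protocol and SAP, Study Design, item 8.

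- **Aim 3 level:** "Assuming $\alpha=0.17$ (conservative adjustment for 3 outcome variables".
- **Aim 3 power:** "controlling for other variables contributing an R2 of .3, we will have power greater than .99 to detect an R2 of 0.2422 or larger".
- **Model being powered:** "in the model predicting smoking topography and cig/day from cue-induced craving and attentional bias change scores". The opening of item 8 defines smoking topography as latency to light and puff volume. With cigarettes per day this makes three outcomes, the same three as in the Aim 2 MANCOVA.
- **Level used elsewhere in the item:** for Aim 1, "a multivariate $\alpha = .05$, and an R2 of .3 from other covariates in the model"; for Aim 2, "with a multivariate of $\alpha=.05$, 20 subjects per group, and an R2 of .3".
- **Aim 3 analysis:** regressions to see whether changes in craving and attentional bias "predict reductions in smoking topography and daily smoking and elevations in intention to quit and confidence to quit". No test level is given there.
- **Standing of Aim 3:** "The primary analyses (Aims 1 and 2) will be evaluated via repeated measures multivariate analysis of covariance (RM-ANCOVA". Aim 3 is not in that group.

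**The concern.** A conservative adjustment for several outcomes lowers the level at which each one is tested. The printed figure raises it, so the number and its description cannot both be right. No other Aim 3 level appears in the document. An analyst looking for one would find only this figure, and a reader checking the power statement cannot tell which level it was computed at. At stake are the test level for Aim 3 and the traceability of its power figure.

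**Working it through.** **Inputs, from Study Design, item 8:** base level .05 (Aims 1 and 2); three outcomes; 20 per group in four groups, so N = 80, with dropouts replaced; covariate R2 = .3; stated power above .99. The target R2 is printed as 0.2422. I read it as 0.24 followed by a run-in citation number and also try it literally. **Assumptions:** one to four tested predictors and zero to six covariate degrees of freedom, because the plan gives neither.

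**Step 1: the level.**
- Bonferroni: 0.05/3 = 0.0167.
- Sidak: 1 - 0.95^(1/3) = 0.0170.
- The printed value against the base level: 0.17/0.05 = 3.4.
- The printed value against Bonferroni: 0.17/0.0167 = 10.2.
- Other routes: 0.025/3 = 0.0083, 0.10/3 = 0.033, 0.05 × 3 = 0.15. None gives 0.17.

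Both standard adjustments round to 0.017, which differs from the printed figure by one zero.

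**Step 2: the plan's power figure.** The test is a noncentral F test for the added R2, with u tested predictors, k covariate degrees of freedom, N - u - k - 1 denominator degrees of freedom and noncentrality N × f2.

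*Increment reading* (0.24 on top of the covariates' .3): f2 = 0.24/(1 - 0.3 - 0.24) = 0.24/0.46 = 0.522; noncentrality 80 × 0.522 = 41.7.

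*Partial R2 reading*: f2 = 0.24/(1 - 0.24) = 0.24/0.76 = 0.316; noncentrality 80 × 0.316 = 25.3.

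Power with k = 3:

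| Tested predictors | Increment, 0.17 | Increment, 0.0167 | Partial, 0.17 | Partial, 0.0167 |
|---|---|---|---|---|
| 1 | >0.9999 | >0.9999 | 0.9999 | 0.994 |
| 2 | >0.9999 | 0.9998 | 0.9994 | 0.985 |
| 3 | >0.9999 | 0.9994 | 0.9986 | 0.972 |
| 4 | >0.9999 | 0.9988 | 0.9975 | 0.956 |

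Varying k from 0 to 6 moves no entry by more than about 0.001. Taking 0.2422 literally raises power slightly: with three predictors at 0.0167, from 0.9994 to 0.9995 on the increment reading and from 0.972 to about 0.974 on the partial reading.

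**Step 3: what this shows.** On the increment reading, power above .99 is reproduced at both 0.17 and 0.0167, so the printed power does not reveal which level was used. On the partial reading it is reproduced at 0.17 throughout, but at 0.0167 only with a single tested predictor.

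**The case against.** The strongest reply is that nothing follows from the digit. The intended value can be recovered from the text, because the method (a conservative adjustment), the divisor (3) and the base level (.05) are all there. The increment reading is the natural one, since the plan says the covariates contribute their own R2. On it the stated power and N = 80 survive, and Aim 3 is outside the primary analyses. This stands, and it limits the point to a correction.

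A second reply is that the text extraction may have lost a digit. Other numerals in the same paragraph look damaged, with citation numbers apparently fused to values. A fused citation is a different fault from a dropped zero, so the mismatch remains. But whether the authors made it is unproven, and the source should be checked first.

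Three stronger readings are tempting, and the document does not support them.

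- *That Aim 3 has no usable level, or that its outcomes are unnamed.* The power sentence names topography and cigarettes per day, and the same item defines topography as two measures. The background text's "These three measures will be assessed pre-post training" refers to cigarettes per day, intent and confidence. It concerns assessment times, not the Aim 3 adjustment.
- *That Aim 3 will be tested at 17%.* The figure appears only as an assumption of the power calculation, and the analysis text does not adopt it. A family-wise error of about 43% (1 - 0.83^3 = 0.428) would require that use and independent outcomes.
- *That Aim 3 is underpowered.* Power below .99 at 0.0167 arises only on the partial reading with two or more predictors, which the plan does not state.

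**Conclusion.** The point holds as a minor error in the text as printed. An Aim 3 level of 0.17 contradicts its own description, and 0.017 is very probably what was meant. That the number and label disagree is certain; the intended value is a well-supported inference, and the origin of the slip is unknown.

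At 0.0167, power is about 0.999 or more for one to four tested predictors, taking N = 80 and 0.24 as an increment over a covariate R2 of .3. If 0.24 is a partial R2, power is about 0.97-0.99 with one to three predictors and 0.956 with four. Neither case calls for a different sample size, and the primary analyses are not touched.

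The Aim 3 analysis text also lists intent and confidence to quit, which are not in the powered model. Whether they belong to the same family is a separate question for the sponsor. A reader might infer that the divisor must be five, but the document does not say so.

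**What to change.** Check the Aim 3 level against the source document. If 0.17 is confirmed:

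1. Replace it with 0.017 (0.05/3) in the power paragraph.
2. State in the Aim 3 analysis text that this level applies to the regressions on latency to light, puff volume and cigarettes per day.
3. Confirm that the Aim 3 power was computed at this level. If it was not, rerun it, giving the number of tested predictors and saying whether 0.24 is an increment or a partial R2.

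The cost is one number, one sentence and at most one rerun of a power calculation. N = 80 and the design do not change.
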